7.5.2 Recording and Reporting Adverse Events and Serious Adverse Events

The investigator must provide the IND Sponsor and monitoring team appropriate information concerning any findings suggesting significant hazards, contraindications, side effects or precautions pertinent to the safety of the study drug. The investigator will instruct subjects prior to administration of study drug to report any physical changes or new symptoms that they notice during the course of the study.

Non-serious AEs and SAEs related only to prophylactic antibiotics will be reported annually to FDA and NIH Office of Science Policy via an Annual Report (by IND Holder GeoVax) and to IRB via Continuing Review (by clinical study team).

The PI must report all SAEs and deaths, whether or not considered related to study treatment, immediately (within 24 hours of knowledge of event) to GeoVax.

For Serious Adverse Events/Pregnancy, please send completed report form to [contact] or fax to [contact]

In the event of a SAE, the investigator must report:

- Treatment regimen (dosing frequency, combination therapy)
- Protocol description (and number, if assigned)
- Description of event, severity, treatment, and outcome, if known
- Supportive laboratory results and diagnostics
- Investigator's assessment of the relationship of the adverse event to each investigational product and suspect medication

The PI should report any follow-up information as it becomes available.

Adverse events meeting the IRB definition of 'Unanticipated Problem' will be reported to the IRB within 10 working days of investigator determination event meets reporting requirements, or within 5 working days for deaths or life-threatening experiences.

Adverse events deemed serious and related to study drug or study procedures (regardless of expectedness) will be reported to any applicable oversite board at the site within 5 working days of knowledge of event.

Adverse events deemed serious, unexpected (i.e., not described in the protocol, Investigator's Brochure or informed consent documents) and related to study drug must be reported to GeoVax using the SAE Report Form within 24 hours of knowledge of event at contact information listed above. The Sponsor is responsible for reporting any event meeting IND Safety Reporting criteria to FDA. SAEs considered related to antibiotic treatment are considered expected.

7.5.3 Safety Monitoring Committee

The SMC will meet and review safety data (i.e., adverse events reporting, reactions to study drug, deaths, etc.) and protocol deviations at time intervals specified in the SMC Charter and at any other time when it is determined by the SMC or GeoVax that such a review is warranted. The SMC will be comprised of, at a minimum, a Sponsor representative, medical monitor (SMC facilitator), and

investigative site designees from each participating site. Only the investigative site designees will be voting members of the SMC. SMC voting members will be experienced professionals in evaluating safety and efficacy data derived from oncology clinical trials. The medical monitor and Sponsor representative will be part of the SMC but will not be voting members. Observers without voting rights are also allowed to join the SMC meetings. All SMC recommendations will be documented and communicated to GeoVax and the investigators at each study site. Following their review, the SMC will recommend whether or not dosing may continue or the need for modifications to the protocol and/or safety monitoring.

In addition, an ad hoc SMC meeting can be planned on initiative from the Medical Monitor/Sponsor based on the regular surveillance of the safety data and/or upon request from an investigator. The SMC may recommend stopping the study at any time that an unacceptable type and/or frequency of AEs is observed.

8. CORRELATIVE/SPECIAL STUDIES

Special studies to assess safety and efficacy of Ad/PNP with F-araAMP are planned and will be conducted by collaborators at Emory University (with IRB approval at that institution) or outsourced to commercial organizations specializing in testing of this sort. These studies are described in Section 9.1 (Procedures Table) as well as Sections 9.2 and 9.3, and include: 1) blood samples for adenovirus, 2) urine for adenovirus, 3) blood samples for antibody against adenovirus, 4) F-Ade plasma level, and 5) tumor biopsy for studies of PNP activity, histochemistry, tumor growth fraction, and adenoviral distribution. Samples will be shipped to Emory or commercial site with the same strict attention to patient confidentiality described throughout the protocol. Please also see Section 10.

Methods regarding tumor biopsy and analysis, as well as serum F-Ade to be arranged by investigators at Emory or designated subcontractor are described below:

- 1) **Measurement of *E. coli* PNP activity.** Approximately 50 mg of tumor tissue will be obtained using a 3 mm dermal punch from the injected tumor site on day 3 just prior to treatment with F-araAMP. This timing coincides with robust transgene expression observed in our preclinical studies and will allow us to ascertain *E. coli* PNP activity at the beginning of F-araAMP treatment. Tissue samples will be immediately frozen and stored at -80°C. Crude extracts will be prepared and incubated with 50 mM potassium phosphate, 100 µM 6-methylpurine-2'-deoxyriboxide (MeP-dR, a standardized *E. coli* PNP substrate), and

100 mM HEPES buffer (pH 7.4) at a concentration of tumor lysate that results in a linear reaction over the incubation period. The formation of 6- methylpurine will be monitored using reverse phase high performance liquid chromatography (HPLC). Care will be taken to thoroughly homogenize samples in order to release PNP enzyme.

- 2) **Metabolism of F-araAMP.** An important measurement to evaluate effectiveness of vector delivery is to quantify active metabolites in tumor tissue following F-araAMP treatment, with the goal to determine levels of F-Ade produced from F-araAMP by *E. coli* PNP. F-Ade in tumor tissues is activated by purine metabolic enzymes to F-Ade - containing nucleotides (primarily F-ATP) and incorporated into RNA, which is responsible for cell killing action of F-Ade. For this measurement, tumor tissue will be obtained using a dermal punch from the tumor site one hour after the final F-araAMP treatment on Day 5. We have shown in mouse tumor xenografts that F-Ade metabolites are retained in tumor parenchyma for prolonged periods ($t_{1/2}$ greater than 24 hours) and obtaining tumor samples one hour after the final injection of F-araAMP should allow for an assessment of F-Ade tumor levels attributable to cumulative administration of prodrug. Because cellular nucleotides rapidly degrade during extraction of tumor tissue, we plan to measure total F-Ade levels by treating the extract with RNase and phosphatases (in the presence of immucillin, a potent *E. coli* PNP inhibitor) to degrade all F-Ade nucleotides to 2-fluoro-adenosine (F-Ado). We will utilize an liquid chromatography/mass spectrometry (LC/MS) method to measure both F-Ade and F-Ado. Since tumor cells may also contain F-araA nucleotides, we will configure a parallel LC/MS method to measure F-araA. Please note that investigators in this project have access to LC/MS protocols specifically for analysis of nucleoside and related compounds, and over 20 years' experience with measurements of this type.
- 3) **Plasma levels of F-Ade.** It will be important to determine the extent to which F-Ade escapes into the general circulation, and we will monitor systemic release of the compound. Plasma samples will be obtained after F-araAMP injection on Days 3 and 5, and analyzed for F-Ade, F-Ado, and F-araA using LC/MS procedures familiar to our laboratories. In our Phase 1 study, no F-Ade was measurable in plasma with an LC/MS assay of sufficient sensitivity to detect F-Ade at levels approximately 100-fold below the no-observable-adverse effect-level (NOAEL) in rats given the compound daily for 7 days.
- 4) **Tumor growth fraction and effects on the stem cell compartment, and evidence for PNP protein expression.** Tumor punch biopsies obtained above will also be studied by histochemistry for markers of active cell cycling (e.g., Ki67) or the tumor stem cell

compartment (e.g., SOX2, Nanog, Oct-4, CD44+/CD24+). Comparisons will be made to original (pretreatment) tumor sections. We will also use the biopsy samples to evaluate levels of PNP expression and adenoviral localization by immunohistochemistry with antibodies to the transgene uniquely available in our laboratory. A portion of each biopsy (e.g., 10%) will be placed in RNA-later for analysis of the same antigens by RT- PCR.

9. STUDY CALENDAR

9.1 Study Procedures Table

Enrolled subjects will follow the schedule of evaluations provided below.

Visit	1	2	3	4	5	6	7	Cycles 1-5 (28-day cycles) ¹²		Cycle 5 or last cycle
								1	2	
Day	Screen -30 to 0	1	2	3	4	5	14± 2	28 ±3	56 ±3	
Informed Consent	X									
Medical History	X									
Physical examination ¹	X	X								
Vital Signs ¹⁶	X	X	X	X	X	X	X	X	X	
Inspect injected tumor site(s)			X	X	X	X	X	X	X	
Performance Status	X	X								
ECG	X								X	
CXR (If no chest CT)	X									
Chemistries ²	X	X ⁸						X	X	X
Hematology ³	X	X ⁸						X	X	X
CD4/CD8 T-cell subsets	X			X ¹¹						X ¹¹
Urine analysis	X									X
Serum pregnancy	X									
PT/aPTT	X									
CT scan/MRI ⁴	X							X		(X)
Physical measurement of tumor size ⁵	X	X				X	X	X	X	
Blood samples for Adenovirus ⁶		X	X							
Urine for adenovirus ⁶		X	X							
F-Ade plasma level				X ⁹		X ⁹				
Blood sample for antibody to adenovirus		X ¹⁰							X ¹⁰	
Intratumoral administration Ad/PNP ⁷		X	X							
PJP Prophylaxis ¹³		X								X
Tumor Biopsy ¹⁴				X		X	X			
Infusion of F-araAMP				X	X	X				
Adverse Events		X	X	X	X	X	X	X	X	
Medications ¹⁵	X	X	X	X	X	X	X	X	X	

1. A thorough physical examination will be done at screen and second study visit; system-oriented examination will be conducted as needed on other visits. Weight and height should be recorded at baseline. Injected tumor will be examined at each visit.
2. Chemistries include: Na^+ , K^+ , CO_2 , Cl , glucose, Mg^{++} , Ca^{++} , blood urea nitrogen (BUN), creatinine (Cr), phosphorus, albumin, alkaline phosphatase, ALT, AST, total bilirubin, total protein.
3. Hematology values include CBC with differential and platelet count.
4. CT or MRI Imaging is to be done in all subjects at Screen and at Visit 7 of the first, second (if PD after first cycle), third, and last cycle. Subjects with CR, PR, or SD in the injected tumor at Day 14 of the fifth or last cycle will have imaging on Day 56.
5. For injected tumors palpable on physical examination, tumor size is to be assessed by physical measurement (ruler or calipers), if possible.
6. Samples will be collected prior to the first administration of Ad/PNP on Day 1 and 2 (± 1 hour) hours after the third administration on Day 2 of the first and third cycle.
7. Ad/PNP will be administered intratumorally three times: two administrations 3-6 hours apart on Day 1 and 1 administration early (morning) on Day 2. Subjects will be monitored continuously for 1 hour after each administration.
8. Blood sample to be drawn and routine chemistry and hematology results reviewed by the Clinical Investigator prior to administration of study drug.
9. Draw two blood samples for F-Ade: one prior to F-araAMP infusion and one 15-30 minutes after infusion of F-araAMP on Days 3 and 5 of the first and third cycle.
10. Blood sample for antibody to be drawn prior to first administration of Ad/PNP on the first and third cycle, and Day 28 of the last cycle.
11. Blood sample to be drawn prior to first infusion of F-araAMP on the first cycle and Day 56 of the last cycle.
12. Evaluations on Visit 2 through 7 are to be done for each 28-day cycle.
13. Prophylaxis for *Pneumocystis jiroveci* (PJP) extends pre-dose dose on Day 1 of cycle 1 through Day 56 following the last cycle. This will be one double-strength trimethoprim (TMP)/sulfamethoxazole (SMX) (i.e., 160 TMP/800 SMX) three times a week.
14. Biopsy of injected tumor will be done on Days 3 and 5 of the first cycle and on Day 14 of the third cycle.
15. Medications will be recorded at screening and any change in medications will be recorded at study visits.
16. Vital signs will be recorded at 30 \pm 15 min, and 60 \pm 15 minutes following each administration

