9.2.5 Visit 7 (Days 14 ± 2)

- Record vital signs
- Examination of injected tumor site(s)
- For injected tumors palpable on physical examination, measurement with calipers or rulers, if possible
- Obtain blood specimen for hematology and chemistry parameters
- Assessment of tumor with CT scan or MRI on first, second (if PD after first cycle), third and last cycle.
- Obtain tumor biopsy, third cycle only.
- Record any AEs.
- Record any change in medications.

Following Visit 7 of the Last Cycle**9.2.6 Visit 8 (Day 28 ± 3 of the Last Cycle)**

- Examination of injected tumor site(s)
- Record vital signs
- Record any new or resolution of adverse events
- Record any change in medications
- For injected tumors palpable on physical examination, measurement with calipers or rulers, if possible
- Blood specimen for:
 - Hematology
 - Chemistry
 - Antibody to adenovirus (last cycle)

9.2.7 Visit 9 or Termination Visit (Day 56 ± 3 of the Last Cycle)

- Examination of injected tumor site(s)
- Record vital signs
- Record any new or resolution of adverse events
- Record any change in medications
- For injected tumors palpable on physical examination, measurement with calipers or rulers, if possible
- ECG
- Obtain blood specimen for:
 - Hematology
 - Chemistry

- CD4/CD8 T-cell counts
- Urine analysis
- MRI or CT scan for subjects who had CR, PR, or SD following last cycle

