9.3.5 Radiographic Imaging

Lesions will also be assessed qualitatively using MRI or CT scan with the site's available MRI and CT techniques. The same imaging technique will be used for all evaluations. The target lesions and injected tumors for intratumoral administration will be assessed radiographically at baseline and within 2 weeks of Ad/PNP-F-araAMP on the first, third, and last cycle (and during the second cycle for those showing PD). In subjects who have CR, PR or SD on imaging 2 weeks after the last drug administration, follow-up imaging will be obtained again approximately 6 weeks later. Non-neck tumor sites may be followed by conventional CT/MRI.

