#### 6.2.2.1 Best Overall Response, Objective Response Rate and Durable Response Rate

##### **Best Overall Response**

Separately for injected tumors and overall (per RECIST v1.1), a participant's best overall response (BOR) is determined by the highest qualitative value assessed during the study for the following hierarchy of objective response results: CR > PR > SD > PD > NE. In order for a valid value of SD to be assigned, there must be evidence of stable disease for at least 6 weeks. If the minimum time for SD has not been met on the first assessment, the assignment of BOR will depend on subsequent response assessments. Participants which do not have follow up data after a first assessment of SD prior to the minimum time requirement will be considered as not evaluable (NE). BOR will be based on assessments collected after the first intratumoral injection until disease progression; assessments collected after the start of new anticancer treatment will not be considered. Confirmation of response will not be required for BOR. Participants who do not have any post-baseline results for response will be considered as not evaluable (NE).

Separately for injected tumors and overall (per RECIST v1.1), BOR will be summarized using the efficacy evaluable population.

Waterfall plots of BOR results for each criterion will be presented graphically using maximum percent reduction. Swimmer plots identifying participant response patterns over time will also be separately provided.

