#### 6.2.2.2 Progression Free Survival

Separately for injected tumors and overall (per RECIST v1.1), PFS is defined as time from first intratumoral injection to date of progression or death for any cause, whichever occurs first, and is calculated, in months, as:

$$(\text{Date of first PD or death or censoring} - \text{date of first intratumoral injection} + 1) / 30.4375.$$

PFS derivation will not include tumor assessments collected after the end of study treatment as these are not planned for collection beyond the final cycle. Tumor assessments taken after switch to another anti-cancer therapy will be excluded from consideration.

The first date of PD would be the earliest date of any post-baseline response finding of progressive disease or death unless a participant is censored at an earlier date. If an assessment occurs over several days, the date of assessment as collected on the Response Assessments eCRF page will be used. If there are no adequate assessments for a participant, they will be censored on their first intratumoral injection date unless they died prior to having their first assessment (in which case the death would be treated as an event). If a participant receives subsequent anticancer therapy prior to documentation of progressive disease, PFS will be censored at the latest adequate assessment prior to additional therapy initiation. Otherwise, if a participant does not have documented progression within this PFS observation period (i.e., until any PFS event or censoring), the participant will be censored at the latest adequate assessment.

Separately for injected tumors and overall (per RECIST v1.1), PFS will be analyzed based on Kaplan-Meier methods; Kaplan-Meier curves will be plotted over time. The number and percentage of participants identified to have had a PFS event and those who were censored will be displayed. The median time to PFS and its corresponding 95% CI will also be produced.

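### Participants whose stop is decided after Day 14 of cycle 2 or 4 may have no scan beyond cycle 1 or 3, and the Day 56 back-up scan has three different triggers

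*Protocol*

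**What the plan says.** **Scheduled scans.** Footnote 4 of the protocol's Study Procedures Table (9.1) places CT or MRI at screening and "at Visit 7 of the first, second (if PD after first cycle), third, and last cycle". Protocol 9.2.5 and 9.3.5 and SAP 6.2.2 follow the same pattern. Cycles 1 and 3 are always scanned. Cycle 2 is scanned only after progression in cycle 1 or if it is the last, and cycle 4 only if it is the last.

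**The scan after treatment.** Its condition is worded three ways:
- Protocol 9.1, footnote 4: "Subjects with CR, PR, or SD in the injected tumor at Day 14 of the fifth or last cycle will have imaging on Day 56". The method of judging status is not named.
- Protocol 9.3.5: for subjects with "CR, PR or SD on imaging 2 weeks after the last drug administration, follow-up imaging will be obtained again approximately 6 weeks later".
- Protocol 9.2.7: "MRI or CT scan for subjects who had CR, PR, or SD following last cycle". Neither Day 14 nor imaging is mentioned.

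**Visits after an early stop.** Protocol 4.2 expects the Day 28 and Day 56 visits of the last treatment cycle, and 3.4 asks those who withdraw early from treatment to complete Day 56.

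**Use of the data.** SAP 6.2.2 evaluates response in combination with CT or MRI at the protocol timepoints, including Day 56. SAP 6.2.2.1 requires 6 weeks for stable disease. Participants who "do not have follow up data after a first assessment of SD prior to the minimum time requirement" are not evaluable (NE). Under SAP 6.2.2.2, if no progression is documented, "the participant will be censored at the latest adequate assessment". The same section leaves tumor assessments made after study treatment out of PFS, and the RECIST part of 6.2.2 rules out PFS follow-up beyond the treatment period.

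**The concern.** For cycles 2 and 4, the scan depends on knowing at Day 14 that no further cycle will follow. The protocol lets some of those decisions fall later. Day 28 is Day 1 of the next cycle (9.2.1), laboratory results are reviewed that day before dosing (9.1, footnote 8), and unresolved high-grade toxicity is judged at Day 1 of the subsequent cycle (4.3). By then Visit 7 has passed.

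A site that follows the schedule literally can then leave cycle 2 or 4 unscanned. On the strictest trigger (9.3.5), the missing scan also removes the qualification for the Day 56 scan. Where the stop was for toxicity or clinical decline, the missing assessment, and the PFS censoring that results, may be informative. The secondary objective concerns the activity of repeat administration, and these participants would have no imaging after their last cycle.

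**Working it through.** **1. Calendar.** Inputs are 28-day cycles (protocol 4.2) and the visit days in 9.1. Study day = 28 × (cycle − 1) + cycle day.

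| Stop after cycle | Last scan sure to be scheduled | Visit 7 of that cycle | Day 56 visit | Gap if Visit 7 is unscanned |
|---|---|---|---|---|
| 1 | 14 | 14 | 56 | none: always scanned |
| 2, no PD after cycle 1 | 14 | 42 | 84 | 84 − 14 = 70 days |
| 3 | 70 | 70 | 112 | none: always scanned |
| 4 | 70 | 98 | 140 | 140 − 70 = 70 days |
| 5 | 126 | 126 | 168 | none: known to be last |

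If Day 28 is counted as the next Day 1 (a 27-day offset), the gaps are 83 − 14 = 69 and 137 − 68 = 69 days.

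**2. Day 56 trigger when the last cycle's Visit 7 was not scanned.**
- 9.3.5: not met, because there is no image to classify.
- 9.1, footnote 4: can be met if caliper status is accepted, which needs a palpable, measurable injected tumor.
- 9.2.7: can be met if some status after the last cycle is recorded.
- None of the three covers unknown status.

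**3. Consequences if no later assessment is counted.**

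*Stop after cycle 2:*
- Stable disease at Day 14 is short of 6 × 7 = 42 days, so best overall response (BOR) is NE.
- PFS without an event is censored at 14 / 30.4375 = 0.46 months.
- A response first seen at Day 14 has DOR censored at 14 − 14 + 1 = 1 day and may fail the 28-day durable criterion.

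*Stop after cycle 4:*
- Stable disease at Day 70 exceeds 42 days and is kept.
- PFS without an event is censored at 70 / 30.4375 = 2.30 months.
- A response present at Days 14 and 70 spans 70 − 14 + 1 = 57 days, which exceeds 28.
- Only a response first seen at Day 70 would have one-day DOR (70 − 70 + 1 = 1).

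**4. Objective response rate.** The plan's own figures reproduce. With 10 evaluable participants and rejection at 3 or more responses, the exact binomial gives alpha P(X ≥ 3 | 0.10) = 0.070 and power P(X ≥ 3 | 0.40) = 0.833, against the stated 7% and 83%.

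The documents give no distribution of stopping cycles. As an assumption, let a share m of all true responders have a response that only a missed scan would have shown, and count them as non-responders. Power is then P(X ≥ 3 | 0.40(1 − m)) and alpha is P(X ≥ 3 | 0.10(1 − m)).

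| m | 0 | 10% | 20% | 30% | 40% | 50% |
|---|---|---|---|---|---|---|
| Power | 0.833 | 0.760 | 0.669 | 0.562 | 0.444 | 0.322 |
| Alpha | 0.070 | 0.054 | 0.040 | 0.028 | 0.019 | 0.012 |

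The error is in the conservative direction. The table shows sensitivity and does not predict m.

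**The case against.** The best defence is that the gap is narrow and partly covered.

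- **Many stops cause no gap.** Cycles 1 and 3 are always scanned, cycle 5 is last by definition, and cycle 2 is scanned after progression in cycle 1. Progression of the injected tumor, a named reason to stop in protocol 4.2, can be found by calipers at Visit 7 in time to order the scan. This stands. A reader might infer that the last cycle is usually recognized only afterwards, but the documents say nothing about how often that happens.
- **The Day 56 scan may still be done.** On the 9.2.7 wording, and arguably under footnote 4, no Day 14 image is needed. This stands in part. One may not conclude that no further scan will be taken, only that it depends on which section the site follows.
- **Caliper data remain.** Palpable injected tumors are measured on Days 1, 5, 14, 28 and 56, and injected-tumor response is the primary focus of efficacy. This limits the gap but does not close it. The SAP evaluates response in combination with CT or MRI, radiologic guidance of injection is allowed (4.2), so some injected tumors may not be palpable, and calipers do not give overall RECIST status.
- **The endpoints are secondary.** That is true, and it limits the weight of the point.

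**Conclusion.** The point holds as a limited defect in the schedule. It concerns participants whose stop is decided after Day 14 of cycle 2 (without earlier progression) or of cycle 4. They may have no scan for up to about 70 days before their last visit, and the protocol has no dependable rule to recover it.

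It would go too far to say that their outcome is lost. A response already seen stays in BOR because confirmation is not required, the participant stays in the response-rate denominator, and deaths still count for PFS and OS. What may go undocumented is a later response or progression. The NE classification of stable disease and PFS censoring at Day 14 apply only to cycle-2 stoppers and should not be read across to cycle 4.

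The conclusion assumes nominal 28-day cycles and a site that follows the schedule literally. The number affected is unknown. The SAP also draws on a protocol clarification letter that is not among the documents, although the SAP repeats the same imaging schedule.

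**What to change.** Reconcile protocol 9.1 footnote 4, 9.2.5, 9.2.7 and 9.3.5 with SAP 6.2.2, using one rule:

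> If no CT/MRI was done at Visit 7 of the cycle that proves to be the last, obtain it at Visit 8 (Day 28) or Visit 9 (Day 56) of that cycle. Day 56 imaging applies to every participant without documented PD, whether or not a Day 14 scan exists.

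The protocol change alone would not repair PFS. In SAP 6.2.2 and 6.2.2.2, state that these scans and the planned Day 56 scan count for BOR, durable response, DOR and PFS. Remove or amend the exclusion of tumor assessments made after study treatment, and the statement that there is no PFS follow-up beyond the treatment period. Tying the scan to Visit 8 or 9 also avoids SAP 5.4, under which unscheduled visits are listed but not summarized.

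The cost is wording in both documents. The plan already intends a last-cycle scan for everyone, and these visits already exist. The small downside is a later scan date for these participants.

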### **Response Per RECIST v1.1 Criteria Details**

Response status per RECIST v1.1 will also be assessed by the investigator using all lesions (target, non-target, and new [if present]) as part of each evaluation. Post-baseline evaluation CT or MRI imaging (per RECIST) is to be done in all participants at Screening and at Visit 7 of the first, second (if PD after first cycle), third, and last cycle. Participants with CR, PR, or SD in the injected tumor at Day 14 of the fifth or last cycle will have imaging on Day 56. There will be no PFS follow up beyond the treatment period. RECIST v1.1 results will be assessed by the investigator

and entered into applicable eCRF pages, including separate assessment of response for overall, target lesions, and non-target lesions.

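### The Day 56 scan condition is written two ways, and tying it to the injected tumor can make censoring of overall PFS informative

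*Protocol*

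**What the plan says.** **Condition tied to the injected tumor.** For the Day 56 scan, footnote 4 of Protocol 9.1 reads "Subjects with CR, PR, or SD in the injected tumor at Day 14 of the fifth or last cycle will have imaging". SAP 6.2.2 has the same condition in its opening text and again in the part on overall response: "Participants with CR, PR, or SD in the injected tumor at Day 14 of the fifth or last cycle will have imaging on Day 56". SAP Appendix 2 reproduces the footnote.

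**Condition not tied to the injected tumor.** Protocol 9.2.7 (Visit 9) lists "MRI or CT scan for subjects who had CR, PR, or SD following last cycle". Protocol 9.3.5 plans a further scan some 6 weeks on, with this condition: "In subjects who have CR, PR or SD on imaging 2 weeks after the last drug administration".

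**Use of the scan.** SAP 6.2.2 states "There will be no PFS follow up beyond the treatment period". SAP 6.2.2.2 leaves assessments made after study treatment ends out of PFS, giving as its reason that none are planned past the final cycle. Without documented progression, "the participant will be censored at the latest adequate assessment". SAP 6.2.2.5 applies analogous censoring to DOR.

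**Two assessments, one stopping trigger.** PFS and DOR are analysed separately for injected tumors and overall. Injected-tumor PD uses only the injected lesions. Overall response uses all target and non-target lesions, whether treated or not, and SAP 3.1 accepts that some target tumors may go untreated. Under Protocol 2.5 and 4.2, progression of the injected tumor ends treatment, so that cycle becomes the last.

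**The concern.** The last scan serving the overall endpoint is, in footnote 4 and the SAP, decided by the status of a different endpoint. A participant whose injected tumor has grown past its threshold while overall disease is still stable stops treatment, so no later-cycle scan follows, and does not qualify for the Day 56 scan. For overall PFS that participant is censored at the scan that showed the local growth.

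Kaplan-Meier estimation treats censored participants as having the same future risk as those still followed. Injected lesions are target lesions under the SAP, so their growth already counts in the overall sum, and it is plausible that these participants are nearer to overall PD than the rest. If so, the overall PFS curve and median are pushed up, as is DOR for any overall responder in this position.

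Sites also have two versions of the rule. Those following 9.2.7 or 9.3.5 could scan a participant whom footnote 4 would leave unscanned, so ascertainment could differ by site.

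**Working it through.** **1. The plan's own interval.** Protocol 9.3.5 puts the follow-up scan about 6 weeks after the Day 14 scan. 56 − 14 = 42 days = 6.0 weeks. With the ±2 and ±3 day windows the range is (56 − 3) − (14 + 2) = 37 to (56 + 3) − (14 − 2) = 47 days. The figure reproduces. When the last-cycle Day 14 scan shows injected PD without overall PD, the participant is censored about 6 weeks before others with the same last cycle. If that happens in an early cycle, the scans of later cycles are lost too.

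**2. Can the two statuses differ?** Assume one injected lesion of 30 mm, 40 mm of stable other target disease, no new lesions, and the same 20% threshold applied to the sum. Growth to 36 mm is injected PD (+20%), but the sum goes from 70 to 76 mm: 6/70 = +8.6%, which is not overall PD. Overall PD needs 0.20 × 70 = 14 mm of growth, or 14/30 = 47% in the injected lesion. Where every target lesion is injected, this route to discordance closes.

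**3. Does Day 56 count for PFS?** The last planned infusion is Day 5, so Day 56 is 51 days after it and the last-cycle Day 14 scan is 9 days after it. Three readings of SAP 6.2.2.2 are possible:
- Treatment ends at the last dose. Day 56 is out, but so is the Day 14 scan that would show the progression.
- Treatment ends with the 28-day cycle. Day 14 is in, Day 56 is out.
- The final cycle covers the calendar columns for cycle 5 or the last cycle. Day 56 is in.

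The SAP does not choose among them.

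**4. Size at the final scan, if Day 56 counts.** All inputs here are assumptions. Let m participants without overall PD share the same last cycle; k of them have injected PD. Let qd and qc be the risks of overall PD by Day 56 in the k and in the other m − k.
- Conditional scan: the k are censored at Day 14, so the Kaplan-Meier step is 1 − qc.
- Everyone scanned: 1 − [k·qd + (m − k)·qc]/m.
- Overstatement: (k/m)(qd − qc).

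| m | k | qc | qd | Conditional | All scanned | Overstatement |
|---|---|---|---|---|---|---|
| 8 | 2 | 0.30 | 0.30 | 0.70 | 0.70 | 0 |
| 8 | 2 | 0.30 | 0.50 | 0.70 | 0.65 | 0.05 |
| 8 | 2 | 0.30 | 0.70 | 0.70 | 0.60 | 0.10 |
| 8 | 2 | 0.30 | 0.90 | 0.70 | 0.55 | 0.15 |
| 8 | 2 | 0.50 | 0.30 | 0.50 | 0.55 | −0.05 |

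With qc = 0.30, m from 5 to 10, k from 1 to 3 and qd from 0.5 to 0.9, the extremes are (1/10)(0.2) = 2 points and (3/5)(0.6) = 36 points.

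**5. Cross-check over the whole schedule.** A simulation took 10 participants, assumed median times of 90 days to injected PD and 120 days to overall PD, and used scans at Days 14, 56 + 14 = 70 and 112 + 14 = 126, with a final scan 42 days after the last (Day 168 after five cycles). It had no deaths, no new therapy and no cycle 2 scan. The true overall PFS at Day 168 is 0.5^(168/120) = 0.379. With the injected-tumor condition, the mean Kaplan-Meier estimates were 0.389, 0.430, 0.470 and 0.506 for correlations of 0, 0.3, 0.6 and 0.9 between the two times. The excess is 1, 5, 9 and 13 points. Giving the discordant participants the one Day 56 scan changed the estimates to 0.343, 0.373, 0.394 and 0.394. That is closer to 0.379 at each positive correlation, but 4 points below it at zero, because those participants are then scanned at different times from the rest.

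**The case against.** The strongest objection is that the effect on PFS may not exist. Under the second reading in step 3, Day 56 enters PFS for nobody, and by analogy DOR, so the differential effect of that scan is zero. This stands as a possibility. It does not remove the loss of later-cycle scans when injected PD ends treatment early, and the ambiguity itself needs settling.

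Second, a reader might infer that the Day 56 scan is given only when the injected tumor has not progressed, that it supplies overall PFS and DOR, and that overall PFS is therefore overstated. The documents do not support that as a flat statement. Protocol 9.2.7 and 9.3.5 would allow the scan for a participant with overall SD. The SAP does not settle whether the scan counts. Upward bias needs some discordant participants, and a higher risk of overall PD among them. Deaths can still count as events. Larger figures follow if every discordant participant is assumed to progress overall at the very next scan, but nothing in the documents supports that.

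Third, footnote 4 provides a cycle 2 scan after PD in cycle 1, so imaging need not stop at once for those participants. This stands in part. The footnote does not say whether injected or overall PD is meant, or how a cycle 2 visit fits with injected progression ending treatment. Those passages must be reconciled.

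Fourth, counting injected PD as an overall event makes a different composite endpoint. That is correct, so such an analysis is a bound and not a replacement.

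**Conclusion.** The inconsistency is certain: footnote 4, SAP 6.2.2 and SAP Appendix 2 limit the Day 56 scan by injected-tumor status, Protocol 9.2.7 and 9.3.5 do not, and SAP 6.2.2.2 does not make clear whether that scan counts.

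The bias is likely but conditional. It requires participants with injected PD and no overall PD whose risk of overall PD exceeds that of the others. The first is possible under the plan's definitions and the second is plausible; the documents quantify neither. If Day 56 counts, the central assumed case gives 5 to 15 points on overall PFS at the final scan. DOR is touched only in an overall responder with discordant status, and no size was calculated for it.

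The consequence is limited. Overall PFS and DOR are secondary, descriptive summaries in about 10 evaluable participants, and ORR for injected tumors, the efficacy endpoint of main interest, is not affected. In a group that small, though, one or two such censorings can visibly move the curve.

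**What to change.** 1. Reconcile footnote 4, SAP 6.2.2 and SAP Appendix 2 with Protocol 9.2.7 and 9.3.5, so that the Day 56 imaging condition serving the overall endpoint refers to overall status as well as injected-tumor status. State which PD triggers the cycle 2 scan.
2. State in SAP 6.2.2.2 and 6.2.2.5 whether the Day 56 scan counts for PFS and DOR, and define the end of study treatment for that purpose.
3. Report how many participants had overall imaging end because of injected PD without overall PD. Add one Kaplan-Meier sensitivity analysis of overall PFS that counts them as events at that date, labelled as a conservative bound.

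Cost: SAP and protocol wording and one more Kaplan-Meier run. Item 3 needs no extra scan. If the condition is widened, the few discordant participants have one scan at a visit already scheduled. That would reduce the bias without removing it: anyone who starts new anticancer therapy first is still censored before the scan, and discordant participants would be imaged at different times from the rest.
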